11.1 Statistical Analysis

Interrupted Time Series Analysis

Design

Each intervention GP practice will be matched one-to-one with a control practice according to the characteristics described above. At least 12 months of outcome data before, and following, the index date will be available for analysis.

[figure not shown]
Descriptive statistics

Characteristics of intervention and control practices and their patients, and those that crossed over or declined the intervention, in terms of variables used for matching and all outcome measures, will be compared descriptively and inferentially in the pre-intervention period using t-tests for continuous and Fisher's exact tests for categorical variables. Outcome measures will be plotted as monthly time series of events across the pre- and intervention periods.

Modelling

To analyse binary patient-level outcomes, including our primary outcome measure (proportion of delayed urgent and emergency online consultations; proportion of delayed urgent online consultations; proportion of delayed emergency online consultations; proportion of online consultations cancelled by patients; proportion of online consultations assigned to clinicians), we will use mixed-effects logistic regression models with appropriate offset terms (number of urgent and emergency online consultations). We will initially analyse data as a time series with a minimum of 12 time points (months) pre-intervention and 12 intervention. The main exposure of interest will be membership to the intervention or control group modelled as binary (0/1). Models will be adjusted for practice characteristics that we have been unable to match during randomisation described elsewhere (e.g. patient population size). Where possible, we will also adjust models for the following practice characteristics that may influence the primary outcome measure: length of time using PATCHS without AI Triage, and other features enabled in PATCHS (the system has several configurable features such as different AI modules). Time will be modelled as continuous (1 to 24) to account for trends in the pre-intervention period. We will also attempt to include month as a categorical variable to account for seasonality. The main parameter of interest will be the interaction term between practice group (intervention vs control) and study period (pre- vs intervention); post-estimation commands will be used to obtain estimates for each study period by practice group.

To analyse continuous patient-level outcome measures (absolute time to completion or staff user action for urgent and emergency online consultations – combined and separate; absolute time to completion or staff user action for routine online consultations) we will use mixed-effects linear regression models with all other aspects of the analysis remaining the same.

If multiple online consultations are submitted by the same patient, we will randomly sample one per patient for analysis. Multiple online consultations from the same patient are expected to be infrequent, though if this approach adversely affects reaching our sample size target we will instead include all online consultations with a patient-level variable in our models.

To analyse count GP practice-level outcome measures (proportion of total appointments provided by GP practices; proportion of online consultations submitted by patients; proportion of patients with emergency department attendances; proportion of online consultations with emergency department attendances; proportion of patients with emergency hospital admissions; proportion of online consultations with emergency hospital admissions) we will use negative binomial regression models with appropriate offset terms for the denominators. For example, GP practice population size (40) or number of whole-time equivalent GPs per 1000 patients (39).

[figure not shown]
Cost consequences of clinician, emergency department, and hospital admission contacts will be estimated by multiplying counts by the relevant weighted average unit cost (42). The timeframe for the cost consequences analyses will be limited to the 12-month period of implementation in the study. Impacts on health and wellbeing outcomes will not be evaluated due to the variety of different health-related reasons patients may present with, resources required to collect health-related quality of life measures via primary data collection, and the retrospective nature of the pre-intervention period evaluation. PATCHS is delivered across both comparator and treated practices so the cost of PATCHS itself will not feature in the economic analyses. The costs of the intervention include the AI element of PATCHS and training of this element to practices (funded centrally). We will explore the identification of these costs and, where feasible, the apportioning of these costs to practices. To analyse continuous GP practice-level outcome measures (cost of processing online consultations within the GP practice per 1000 patients; cost of emergency department attendances and emergency hospital admissions per 1000 patients) we will use linear regression models with all other aspects of the analysis remaining the same.

Sensitivity analyses

Limitations with the above approach include that: staff triage decisions could be applied by non-clinicians which could be systematically different to those applied by clinicians (43); we assume that patients who receive a signpost message and cancel their online consultation have not experienced a care delay; and the triage decisions made by GP practice staff may be highly variable. We will therefore conduct sensitivity analyses where: we restrict triage decisions to those only made by clinicians; we exclude patients who receive a signpost message and cancel their online consultation; we define online consultations as urgent and emergency in intervention and control practices if they are predicted as either 'urgent' or 'emergency' by Al Triage. We will also conduct sensitivity analyses where we sub-sample practices and patients with similar: baseline levels of the outcome measure, monthly volume of online consultations per 1000 patients, prevalence of urgent and emergency online consultations, agreement with AI Triage predictions, contributions to AI Triage model training, and other variables matched during randomisation and model adjustment where appropriate. Further sensitivity analyses may be undertaken based on findings from the process evaluation (44), for example, we may find a cohort of practices that did not engage with the Al Triage training, and we may test the hypothesis that Al Triage was less effective at reducing delays in urgent and emergency online consultations for them. We will also explore using an alternative analysis approach, interacting practice group with time and period to estimate the adjusted intervention time series. For example, a difference-in-difference method pooling the outcome (and the offset) in the preand intervention periods.

Health inequalities

We will use the pre-intervention period to assess for inequalities in the influence of patient characteristics on experiencing urgent and emergency care delays in both the pre- and intervention periods. We will use

patient age, sex, ethnicity, socioeconomic deprivation, and non-English language usage as predictors in our regression model to compare the probability of experiencing a care delay (45). We will also explore the possibility of adding data on patient multimorbidity and frailty if available. If there is a main effect in the outcome analyses, we will also use sub-group models for appropriate interaction terms in the main models to explore the effectiveness of the intervention on population strata of interest described above. We appreciate power will be lower for these investigations so these approaches will be exploratory, and this approach assumes that there is a main effect for the primary and / or secondary outcomes.

Quantitative Process Evaluation

Fidelity, dose, and reach of AI Triage and online consultations

'Fidelity' is whether the intervention is delivered as intended (44). We will evaluate fidelity through counts of how many practices have AI Triage switched on and the number and proportions of staff in each practice that access online learning materials.

'Dose' is how much intervention is delivered (44). We will evaluate dose through descriptive analyses of counts of online consultation usage submissions in both intervention and control practices in terms of overall numbers and specific types of online consultations (for example, health problems or administrative requests). In intervention practices, we will undertake descriptive analyses of counts of predictions made by Al Triage (urgent, emergency, or routine).

'Reach' is the extent a target audience encounters the intervention (44). We will evaluate reach in both intervention and control practices through descriptive analyses of counts of patients that submit online consultations, how many each they submit, counts of staff that process them (including comparisons between clinical and non-clinical staff), and how many each they process. In intervention practices we will include separate counts of staff that process online consultations that have been predicted by Al Triage as urgent or emergency, and how many patients are presented with signpost messages.

[figure not shown]
Al Triage accuracy in intervention GP practices

We will calculate the overall accuracy (proportion of 'correct' predictions), true positive rate, true negative rate, positive predictive value, and negative predictive value of AI Triage in intervention practices. Our primary measure of accuracy will be for urgent and emergency online consultations combined; secondary measures will assess urgent and emergency online consultations separately. There is no gold standard test to decide the 'correct' triage decision for online consultations written by patients in their own words. We will therefore use the triage decisions made by GP practice staff when processing online consultations and consider their triage decision as 'correct'. Where AI Triage predicts an online consultation as 'urgent' or 'emergency' we will consider it a:

- **True positive** if the triage decision is not changed by staff, or if staff change the triage decision and the highest triage decision applied by staff is 'urgent' or 'emergency'.
- False positive if staff change the triage decision and the highest triage decision applied by staff is
 'routine'.

Where AI Triage predicts an online consultation as 'routine', we will consider it a:

- **True negative** if the triage decision is not changed by staff, or if staff change the triage decision and the highest triage decision applied by staff is 'routine'.
- False negative if staff change the triage decision and the highest triage decision applied by staff is 'urgent' or 'emergency'.

We will quantify cases where emergency online consultations have been predicted as 'routine' as these represent the highest risk misclassifications. The Spectra Analytics Clinical Safety team will investigate these and other patient safety incidents reported by GP practices as per their internal processes to comply with MHRA and NHS DCB0129 standards (16). We will review their findings to understand if there are patient groups or online consultation topics that are at higher risk of misclassification by Al Triage.

Potential triage behaviour change in control GP practices

We will obtain AI Triage predictions (urgent and emergency – both separate and combined) for control practices for each online consultation submitted during the intervention period and compare them to the actual triage decisions made by GP practice staff using the same definitions of true/false positives/negatives above. These predictions will differ from those in intervention GP practices because they will not have been presented to GP practice staff whilst they processed the online consultations. It identifies a group of patients for whom potentially different triage decisions would have been made if AI Triage had been enabled in those practices. We will then estimate the potential impact of these different triage decisions.

Observed triage behaviour change in intervention and control GP practices

To evaluate observed changes in triage behaviour, we will compare monthly and weekly time series counts of urgent and emergency triage decisions (both separate and combined) made by intervention and control GP practices. In intervention practices we will consider a triage decision as urgent or emergency if the highest triage applied by staff is 'urgent' or 'emergency' or an AI Triage prediction of urgent or emergency is left unchanged (same definition as 'true positives' above). In control practices, we will consider a triage decision as urgent or emergency if the highest triage applied by staff is 'urgent' or 'emergency'. We will also measure counts of patients cancelling their online consultations, and map whether patients cancel their request or receive input from a clinician following a signpost message and/or emergency prediction.

[figure not shown]
Sensitivity analyses

Similar to the interrupted time series analysis, limitations with the above approach include that: staff triage decisions could be applied by non-clinicians; the true urgency of an online consultation may only be apparent when further information has been obtained from the patient (e.g. over the telephone); we assume AI Triage predictions for patients who receive a signpost message and cancel their online consultation is correct. We will therefore conduct sensitivity analyses where: we restrict triage decisions to those only made by clinicians; the final triage decision when the online consultation is resolved is used; patients who receive a signpost message and cancel their online consultation are excluded. As mentioned above, multiple online consultations from the same patient are expected to be infrequent, though will be assessed by using a patient-level variable in models and by re-running analyses after randomly sampling one online consultation per patient.

Health inequalities

We will assess the potential influence of AI Triage on health inequalities across different age groups, sexes, ethnic backgrounds, Index of Multiple Deprivation quintiles, and non-English language usage. In dose and reach metrics we will compare the proportion of each sub-group in the population using online consultations in intervention and control practices in the pre- and intervention periods (44), and to the characteristics of the wider practice populations in National General Practice Profiles (38).

Each accuracy metric will be tested for differences in performance between patient sub-groups. We will also undertake a failure case analysis to explore factors why AI Triage may have predicted incorrectly (46)

by comparing the characteristics of patients who have submitted online consultations classified as false positive and negatives to those of true positive and negative predictions ('error auditing') (47). Additional factors to test will include those related to the online consultation (including type of online consultation, time and day of submission), GP practice staff who applied the triage decision (including role, experience using PATCHS), and GP practice (including size, geographic location, experience using PATCHS).

In potential behaviour change analyses, we will find patients for whom the AI Triage prediction differs from the actual decision made by GP staff (potential false positives and negatives) and test for differences in characteristics of the patient, online consultation, GP practice staff, and GP practice using the error auditing approach described above (47).

Allocation non-adherence

In a traditional Zelen design, data are analysed on an intention-to-allocate basis rather than whether or not the intervention was actually received (24). This approach is practical when the intervention is not widely available and when participants can provide immediate consent, which is not the case in this study. Firstly, AI Triage has been available to all GP practices using PATCHS since October 2021, therefore control GP practices can start using AI Triage at any time during the study. Because it is considered a selling point, GP practices may also receive communications encouraging them to use AI Triage outside the study e.g. from their NHS commissioning organisation. Secondly, GP practices may take several weeks to reply following an invitation to use AI Triage. Thirdly, GP practices not yet using AI Triage may have explicitly chosen not to use it, meaning they may be more likely to decline an invitation to use it or drop out of the study later. These factors combine to exacerbate our anticipated recruitment challenges described above. Therefore, we will take the following approach:

- Control GP practices that cross over to the intervention group: If we have sufficient follow-up data
 we will treat them as intervention GP practices in the main analysis, otherwise we will use their data
 as controls up to the point they cross over. If numbers allow, we will analyse them separately in an
 uncontrolled interrupted time series analysis. We will conduct sensitivity analyses where we treat
 them control GP practices for the entire study and where we exclude them entirely from the analysis.
- GP practices that decline to use the intervention or do not respond to recruitment communications after being allocated to the intervention group: We will treat them as control GP practices in the main analysis. We will conduct sensitivity analyses where we treat them as intervention GP practices and where we exclude them entirely from the analysis.
- Intervention GP practices that cross over to the control group (i.e. that stop using Al Triage) or stop
 using PATCHS altogether: We will include them in the main analysis in the intervention group. We
 will undertake sensitivity analyses where we use their data as intervention GP practices up to the
 point they cross over and where we exclude them entirely from the analysis.

11.2 Sample Size:

Our sample size calculation is based on our primary outcome measure. Patients and clinicians we consulted during our PPI work felt an absolute reduction of 5% in the proportion of urgent and emergency online consultation delays would be meaningful. Assuming a baseline delay of 25% from our prior research and a simple before-after design, we estimate a minimum of 2928 urgent and emergency (combined) online consultations across both intervention and control GP practices during the intervention period are required to detect a minimum absolute reduction of 5% to 20% with 90% power and 5% alpha. Further assuming 50 urgent and emergency online consultations (combined) on average for a GP practice per month and a 12-month intervention period, this translates to a minimum of three intervention and three control practices. However, this does not account for between-practice variability. Consequently, we will aim to recruit 20 intervention and 20 control practices. Between-practice variability can be difficult to

predict, so we have estimated the power of this sample size for different assumptions of between-practice variance using ipdpower for Stata (48), which calculates power for mixed-effects models using simulations (Table 1). To minimise between-practice variance in our sample, we will recruit intervention and control GP practices in blocks (described in section 8.4). If we find that between-practice variance is high, we will target recruitment of practices with similar baseline characteristics for the outcome measure in subsequent stages.

Table 1: Study power simulations

Between-practice variance	Power (%)	95% confidence interval (%)
0	100	96.4-100.0
0.1	72	62.1-80.5
0.2	53	42.8-63.1
0.825	21	13.5-30.3

12) DATA AND INTERVENTION ACCESS POST-STUDY

Data will be stored on secure UoM Research Data Storage servers for 5 years after publication of our results per UoM's Record Retention Schedule (49). Only the UoM research team will have access to these data during this time. Following consideration of all legal and ethical perspectives, interests and contractual stipulations of third-party funders and other stakeholders, as well as aspects of confidentiality and security, the data will then be deleted using hard drive eraser software. We will document any deletion and destruction of data and make it accessible for possible future audit.

Following the study intervention GP practices can continue to use AI Triage after the study if they wish, and control GP practices will be offered AI Triage. PATCHS (without AI Triage) and PATCHS AI Triage are available for free to all NHS GP practices via the NHS Buying Catalogue (15). All online consultation software solutions on this framework are centrally funded and do not incur any direct cost to individual GP practices or NHS commissioning organisations. In addition, Spectra Analytics will explore the feasibility of creating an application programming interface that enables external organisations to receive predictions from the AI Triage model to validate its outputs using their own datasets.

13) MONITORING AND QUALITY ASSURANCE

The study will be subject to the audit and monitoring regime of The University of Manchester. An independent Study Steering Committee will be appointed to ensure that the project is conducted to rigorous standards. The committee will include academics with appropriate clinical and methodological expertise, and one member of the public. The committee will meet at least three times during the project. As a UKCA-marked medical device already used in routine clinical practice, any safety issues associated with the AI Triage intervention will be reported and managed in the usual way by Spectra Analytics as per UKCA and NHS DCB0129 standards.

The project will be monitored against progression criteria (Table 2) covering recruitment, protocol non-adherence, and outcome data using a traffic light system (9): red/stop (intractable issues that cannot be remedied), amber/amend (remediable issues) or green/go (no concerning issues). Progression criteria will be judged at four months (halfway through) into our planned recruitment period. We anticipate that recruitment will be most problematic. Progress will be reported to the Study Steering Committee. If red or amber criteria are met for recruitment, the following mitigation strategies will be considered and

discussed with the: 1) Study Steering Committee, 2) funder, and 3) NHS Research Ethics Committee and Health Research Authority (if appropriate): approaching more GP practices to aid recruitment; working with industry partners to offer control practices an incentive for deferring that will not impact study outcomes; conduct a prospective uncontrolled interrupted time series analysis; conduct a retrospective controlled or uncontrolled interrupted time series analysis using data from GP practices that previously met the inclusion criteria; or relaxing inclusion criteria.

Table 2: Progression criteria judged at four months into recruitment

Study aspect	Red	Amber	Green
Recruitment	 <10% of total intervention patients recruited* <10% of total intervention GP practices recruited* 	10-50% of total intervention or control patients recruited 10-50% of total intervention or control GP practices recruited	 >50% of total intervention and control patients recruited >50% of total intervention and control GP practices recruited
Protocol non-adherence	 >80% of patients have withdrawn consent to share data >80% of intervention GP practices no longer using the intervention* 	 40-80% of patients have withdrawn consent to share data 40-80% of intervention GP practices no longer using the intervention 40-80% of control GP practices are using the intervention 	 <40% of patients have withdrawn consent to share data <40% of intervention GP practices no longer using the intervention <40% of control GP practices are now using the intervention
Outcome data	Outcome data available for <40% of recruited GP practices Outcome data available for <40% of recruited patients	 Outcome data available for 40-80% of recruited GP practices Outcome data available for 40-80% of recruited patients 	Outcome data available for >80% of recruited GP practices Outcome data available for >80% of recruited patients

^{*}Control patients nor control practices are not included because one mitigation strategy could be to conduct an uncontrolled time series analysis.

14) PEER REVIEW

This protocol has been peer-reviewed as part of the application for funding to NIHR HSDR programme.

15) PATIENT AND PUBLIC INVOLVEMENT (PPI) AND STAKEHOLDER ENGAGEMENT

PPI input to this plan

We conducted interviews with seven patients and held workshops with 10 GP practice staff to gather feedback on our study plans. PPI co-applicants on the funding grant reviewed and edited the grant application including the plain English summary. Changes to our approach based on our PPI work included adding objectives to evaluate the impact of AI Triage on health inequalities and health system resources, selection of the primary outcome measure, and the magnitude of its reduction that would be clinically meaningful.

PPI input during the study

We will recruit a PPI group of six people who will be members of the public who use GP services. The group will meet up to 10 times during the project every 2-3 months. Meetings will be face-to-face or via video conference, though members will also be able to contribute by other means (e.g. email, phone, or post), depending on individual circumstances. In addition to the PPI group, we will also recruit up to six members of staff (GPs, practice managers etc) from GP practices to be part of a separate stakeholder group. This group will meet in a similar way, at a similar frequency. Both groups will contribute to data analysis and project outputs.

16) ETHICAL AND REGULATORY CONSIDERATIONS

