GP practices will be randomly allocated to intervention (AI Triage now) or control (AI Triage later) groups in blocks of 5 practices in each arm (control and intervention) using the *runiform* command in Stata 18 with a target of 20 in each group. Depending on the response rate we may increase or decrease block size, and through a combination of randomisation and algorithmic approaches (31) using appropriate statistical software (32) we will attempt to match the two groups as closely as possible on patient population size (40), Index of Multiple Deprivation (34), monthly volume of online consultations per 1000 patients, baseline levels of the primary outcome measure, and baseline prevalence of urgent and emergency online consultations. We will also explore the possibility of matching GP practices on geographic region, rurality (36), number of whole-time equivalent GPs per 1000 patients (39), mix of patient ethnicities, and levels of patient morbidity (40), though given the target sample size is relatively small this may not be possible. Where we cannot match characteristics, we will attempt to adjust for them in our statistical models.

This is a single-blind study. The UoM research team will not know which GP practices are allocated to intervention or control groups. Due to the nature of the intervention GP practices cannot be blinded. The

UoM research team will randomly allocate GP practices to "0" or "1" groups using the approach described above. The allocation sequence will be provided to Spectra Analytics who will use statistical software to randomly allocate "0" or "1" to be the intervention group. They will then approach GP practices in the intervention group to offer them AI Triage as described elsewhere. Spectra Analytics will retain the mapping key and not share it with the UoM research team until after data analysis is finalised. The interrupted time series analysis (including analysis of the primary outcome measure) will not be undertaken until the end of the intervention period. Analyses will be undertaken by the UoM research team only not Spectra Analytics.

8.5 Participants who withdraw consent or lose capacity to consent:

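### Baseline t-tests and Fisher's exact tests on patient-level data ignore clustering within practices, so they overstate differences between arms and for practices that cross over or decline

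*Protocol*

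**What the plan says.** Under Descriptive statistics, Protocol section 11.1 sets out a pre-intervention comparison. It covers "Characteristics of intervention and control practices and their patients, and those that crossed over or declined the intervention". The variables are the matching variables plus every outcome measure. The method is that they "will be compared descriptively and inferentially in the pre-intervention period using t-tests for continuous" variables; categorical variables get Fisher's exact tests. No aggregation to practice level, random effect or cluster-robust variance is attached to these tests.

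Section 9 labels the primary outcome and several secondary outcomes as patient-level. Section 8.4 makes the practice the randomised unit: "GP practices will be randomly allocated to intervention (AI Triage now) or control (AI Triage later) groups in blocks of 5 practices" per arm. It also attempts to match the arms, and the matching targets include the baseline level of the primary outcome.

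Elsewhere the protocol recognises clustering. The Modelling paragraphs of section 11.1 use mixed-effects models for the same patient-level outcomes, and section 11.2 concedes that its simple calculation leaves out between-practice variability and tabulates power for several variances.

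**The concern.** A t-test or Fisher's exact test on patient records asks whether two sets of independent patients differ. The question here is whether two groups of practices differ. With hundreds of forms per practice, ordinary variation between practices is enough to make such a test significant when nothing systematic separates the groups.

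This matters most for practices that cross over or decline. Under Allocation non-adherence (section 11.1), practices that decline or do not respond are analysed as controls in the main analysis, and control practices that cross over are analysed as intervention practices if follow-up is sufficient. Readers will use the baseline comparison to judge how selective those reassignments were. A p-value that mainly reflects clustering cannot inform that judgement.

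**Working it through.** **Inputs.** Section 11.2 gives a baseline delay of 25%, the practice target ("Consequently, we will aim to recruit 20 intervention and 20 control practices") and the volume ("Further assuming 50 urgent and emergency online consultations (combined) on average for a GP practice per month and a 12-month intervention period"), so 50 × 12 = 600 forms per practice. That volume is a planning figure for the intervention period. I apply it to the pre-period, for which section 11.1 promises at least 12 months of data. Table 1 gives between-practice variances of 0, 0.1, 0.2 and 0.825. The protocol states no error rate for the baseline tests.

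**Reproducing the plan's figures.**
- Sample size per arm = [1.960√(2 × 0.225 × 0.775) + 1.282√(0.25 × 0.75 + 0.20 × 0.80)]² / 0.05² = 1464, so 2928 in total, as stated.
- Scale of Table 1: take the variance v as a random-intercept variance on the log-odds scale. The log-odds difference between 25% and 20% is 0.2877, and SE² = [v + 1/(600 × 0.25 × 0.75)]/20 + [v + 1/(600 × 0.20 × 0.80)]/20. Power Φ(0.2877/SE − 1.96) is 100%, 78%, 51% and 17%, against the stated 100%, 72%, 53% and 21%. All four lie inside the stated confidence intervals, which supports the log-odds reading.

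**False-positive rate with no true difference, unmatched practices.** Design effect DE = 1 + (600 − 1) × ICC, where ICC is the variance of the practice proportions divided by 0.25 × 0.75. The rate is 2[1 − Φ(1.96/√DE)].

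| Variance | ICC | DE | Patient-level test rejects |
|---|---|---|---|
| 0 | 0 | 1.0 | 5% |
| 0.05 | 0.0093 | 6.5 | 44% |
| 0.1 | 0.0183 | 12.0 | 57% |
| 0.2 | 0.0356 | 22.3 | 68% |
| 0.825 | 0.1263 | 76.7 | 82% |

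Example at 0.1: 1.96/√11.95 = 0.567, and 2[1 − Φ(0.567)] = 0.57. Simulation with 20,000 null trials per setting agrees to within about a percentage point, and Fisher's exact test behaves like the pooled two-proportion test. A t-test on the 40 practice proportions stays at about 5%.

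**How far this moves** (variances 0.1, 0.2, 0.825):
- Half of the between-practice variance shared within matched pairs: about 44%, 56% and 76%.
- 80% shared: about 27%, 40% and 63%.
- Unmatched, but 300 forms per practice: 44%, 55% and 75%.
- Five decliners against 20 practices, unmatched (five is an assumption): about 57%, 68% and 83%. With equal forms per practice DE does not depend on the number of practices.

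**Other patient variables.** The protocol gives no ICC for age, sex, ethnicity or completion time. At 600 per practice, assumed ICCs of 0.005, 0.02 and 0.05 give 33%, 59% and 73%.

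**Power at practice level.** For a 0.5-SD difference, the non-centrality is 0.5√(20 × 20/40) = 1.58 on 38 df, giving 34% power at 20 v 20. For 5 v 20 it is 0.5√(5 × 20/25) = 1.00 on 23 df, giving 16%.

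**The case against.** **Unit of analysis.** The paragraph does not say that patient rows are the unit tested. The matching variables in section 8.4 are practice-level values, and many outcomes in section 9 are too; with one value per practice the named tests are not inflated. This stands as a limit. But the text also covers patients and every outcome, and for patient-level variables it names tests that do not suit clustered data. That is more than detail left to an SAP.

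**Matching.** A reader might infer that more than half of such trials would show false imbalance. The documents do not support that without conditions. Matching is attempted and includes the baseline primary outcome, the Table 1 variances are scenarios and not estimates, and 600 forms is a planning assumption. Matching does not help with crossovers and decliners, who select themselves.

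**Steering of adjustment.** A reader might infer that these p-values decide which covariates enter the models. The protocol does not say so: "Models will be adjusted for practice characteristics that we have been unable to match during randomisation", which is settled by what could be matched at allocation.

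**Only check.** It would also be wrong to call this the sole safeguard. Section 11.1 includes descriptive comparison, monthly plots, model estimates by period and group, sub-samples of similar practices, and sensitivity analyses that reassign or exclude non-adherent practices.

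**Primary result.** The effect is the group-by-period interaction in a mixed-effects model. The baseline tests do not enter it.

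**Conclusion.** The point holds for patient-level variables. Run on patient records, the named tests are invalid for comparing groups of practices. At the protocol's non-zero variances the false-positive rate is about 57% to 82% without matching and about 27% to 63% if matched pairs share 80% of the between-practice variance; it is nominal only when that variance is zero. These figures assume a log-odds random intercept, 600 forms in every practice and a 25% mean delay. The damage is to interpretation of the baseline table, above all for crossovers and decliners, and not to the primary estimate. Moving to practice-level tests cures the false positives but leaves low power, so a non-significant result would not establish comparability either. The plan should be changed, but the primary analysis does not depend on it.

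**What to change.** In the Descriptive statistics paragraph of section 11.1:

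- Replace the patient-level t-tests and Fisher's exact tests with practice-level summaries and standardised differences, shown by allocated arm and separately for practices that crossed over or declined.
- If a test is kept, make it valid for clustering: use practice-level values, or a mixed model with a practice random effect. For the matched arms it should respect the pairing. With half the variance shared within pairs, an unpaired practice-level t-test rejects only about 1% of the time, so ignoring the pairs errs in the other direction.
- State that a non-significant result is not evidence of balance.

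The cost is new wording and different table columns, with no new data. Baseline comparisons will be wider and less often significant.
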